Given the dearth of experimental data in GV's with chronic musculoskeletal pain (CMP), we have patterned much of our research in GV's after our research in fibromyalgia (FM), a disorder with a primary symptom of muscle and joint pain in civilians. Our work (9-11) and the work of others (12) suggest that FM pain is produced and maintained by central nervous system (CNS) dysregulation of nociceptive and pain processes. Our work also suggests that phenomena similar to those observed in FM may be occurring in GV's with CMP. Like FM patients, GV's with CMP, 1) are more sensitive to experimental pain stimuli (13, 14), 2) exhibit exaggerated pain responses following acute exercise (13), 3) experience more muscle pain during acute exercise (14) and 4) show augmented brain responses to both painful and non-painful experimental stimuli. These data suggest that some of the same pathophysiological mechanisms involved in FM may be maintaining chronic widespread muscle pain in GV's. Critical unanswered questions include whether promising treatments for CMP in GV's can affect laboratory measures of pain sensitivity and pain regulation and whether these changes relate to clinical improvements. We intend to begin to answer these questions by examining perceptual and brain hemodynamic responses to standardized painful stimuli and documenting their relationships to clinical outcomes before, during and upon completion of a viable, novel treatment for CMP.

There are no known efficacious treatments for GV's suffering CMP. Efficacy studies are needed to begin determining effective treatments for our Veterans following their service of our country. In FM, exercise training (both aerobic and resistance modes) is widely recognized as one of the few consistently efficacious treatments, resulting in improved well-being, increased physical function and in some cases decreased pain (15). One large scale treatment trial of aerobic exercise in GV's with chronic multi-symptom illness showed only modest improvements in pain, fatigue and mental health (16). We believe this trial had several limitations that greatly attenuated the treatment's effectiveness; consequently, it is premature to discount exercise training as a treatment for GV's with CMP. Further, we propose a novel approach that employs progressive resistance exercise training (RET) to treat GV's with CMP, while obtaining objective measures of nociceptive function, brain white matter tract pathways and total physical activity.

In addition to exercise performed as part of a structured training program, physical activity behaviors are important determinants of physical and mental health. Greater total physical activity levels are associated with increased physical function, improved mental health, increased energy and decreased symptoms of chronic pain. To our knowledge, none of the exercise training trials in FM have actually measured the impact of the exercise training on physical activity behaviors during daytime hours outside the intervention. It is plausible that the adoption of a structured exercise training program reduces physical activities performed during the rest of the day, and that this change in total physical activity could affect health outcomes. Objective measurement of physical activity will allow us to determine whether RET increases, decreases or has no impact on total physical activity levels in GV's with CMP. This will allow us to begin to characterize sub-groups who benefit the most from RET (e.g. potentially those GV's that maintain or increase their extra-intervention physical activity). Thus, in addition to supervised RET, we will objectively measure total physical activity levels outside of the intervention using accelerometers before, during and following treatment.

In summary, we propose to determine the efficacy of RET for the treatment of CMP and associated symptoms in GV's. In addition, we will assess the influence of RET on total physical activity, pain sensitivity and regulation, and brain white matter tracts. By applying functional neuroimaging techniques in conjunction with pain psychophysics we will test how the brains of Veterans with CMP respond to sensory stimuli and whether these responses can be modified by exercise training. We plan to use blood oxygen level dependent (BOLD)

and diffusion tensor imaging (DTI) methods to evaluate the function of brain regions involved in pain processing and control and the microstructural properties of white matter tract pathways that connect these regions. In addition, we will determine the influence of RET on extra-intervention physical activity behaviors, testing a critical and unanswered question - whether total physical activity levels change as a result of engaging in a RET program in patients with CMP. The primary goals of this project will be accomplished by comparing GV's with CMP assigned to either RET or wait-list control (WLC) in a randomized controlled trial.

Background and Significance

The problem of musculoskeletal pain in Gulf War illness

More than 50,000 troops returned from the Persian Gulf reporting a myriad of medically unexplained symptoms with no identifiable etiology. Of those Veterans participating in the Gulf Health Registry, the fourth most frequently reported symptom is musculoskeletal pain (17). Clinical and factor analytic procedures established the presence of a chronic multi-symptom illness affecting Veterans following deployment to the Persian Gulf (18). Three categories of symptoms were formed: fatigue, mood-cognition and musculoskeletal pain. Predictive and confirmatory factor analysis verified musculoskeletal pain as one of the three major factors in GV's illnesses (18). Medical Outcome Survey (SF-36) data collected by the Iowa Persian Gulf Study Group (19) indicated that deployed symptomatic Iowa GV's exhibited diminished physical function including large amounts of bodily pain compared to non-deployed Veterans. Data estimating the prevalence of symptoms in 11,441 GV's versus 9,476 non-Gulf Veterans in the National Health Survey of Gulf-era Veterans and their families (1) indicated that twice as many GV's reported muscle (8% vs. 4%) and joint pain (15% vs. 8%) than non-Gulf Veterans. Based on these data, upward of 100,000 GV's (15% of 697,000) report unresolved painful complaints that significantly contribute to their functional impairment. It has been almost 20 years since the conclusion of the first Gulf War and epidemiological studies continue to indicate pain as a disabling problem for GV's (5, 6). Moreover, recent medical record data for soldiers from Operations Enduring Freedom and Iraqi Freedom indicate that CMP in the absence of an identifiable injury is likely to be a significant problem for Veterans of the most recent Gulf War (7). Data from medical care and disability estimates for soldiers returning from Iraq indicate that approximately 56% of possible diagnoses will consist of conditions involving diseases of the musculoskeletal and connective tissue (42%) and/or ill-defined conditions that are based on symptoms (17%) (8). This is a significant, enduring and costly illness that deserves attention.

Can resistance exercise training (RET) be an efficacious treatment for GV's with CMP?

There are no known efficacious treatments for sick GV's who were deployed to the Persian Gulf. In the absence of a clear etiology (e.g. chemical exposure, physical trauma), studies aimed at addressing symptoms and improving the quality of life of our Veterans are needed.

One consistently efficacious treatment for chronic musculoskeletal pain is exercise (20-22). Exercise training has been shown to result in improved physical function, decreased symptoms, increased feelings of energy and decreased feelings of depressed and anxious mood for a host of chronic pain conditions including peripheral arterial disease, widespread pain and fatigue, rheumatoid arthritis and fibromyalgia (21, 22). The most relevant comparison group for GV's with CMP is FM, a disorder with a primary symptom of widespread and medically unexplained muscle and joint pain, occurring predominantly in civilian women (23). In FM, a recent meta-analysis of aerobic exercise training found beneficial effects for physical function ($d = 0.66$ standard deviations), global well-being ($d = 0.49$), and pain ($d = 0.65$) (20). Only 3 RET interventions met criteria for inclusion in the review. Although the RET trials were rated as possessing low methodological quality, the results were promising showing large positive effects for global well-being ($d = 1.43$), depression ($d = 1.14$) and pain ($d = 1.68$) and a moderate positive effect on physical function ($d = 0.52$). Of the 1264 subjects assigned to exercise training, only five adverse events possibly related to exercise were reported and none were reported for strength training. One study noted that "...after the initial phase of training, the patients did not complain of any unusual exercise-induced pain or muscular soreness during the experimental period, and even intensive strength training did not worsen the symptoms". In contrast, exacerbation of symptoms was thought to have a negative impact on adherence, but was poorly tracked and reported. The authors concluded that aerobic exercise training produces important benefits for FM patients and that limited evidence suggests that strength training may have a greater effect on the patients' primary complaints of muscle pain. A recent

review of strength training studies found effects similar to those seen in aerobic training studies. Strength training was associated reductions in pain and fatigue, and improvements in cognition, self-esteem and depressed mood in adults with low back pain, osteoarthritis and FM (22).

Although exercise training is recognized as one of the few consistently safe and effective treatments in CMP, methodological rigor has been poor in many studies. Most studies have used aerobic exercise, with relatively few RET trials. Follow-up of patients and assessment of training volume (progression, intensity, frequency and duration) are also rare and incomplete. In fact, Busch et al. (2008) reported that when considering the intensity and duration of exercise tolerable by FM patients, “...*no study analyzed or reported these in a systematic manner.*” Further, exercise studies in FM have consisted of > 90% female samples, thus our understanding of the impact of exercise on widespread pain in males is limited.

We are aware of only one exercise training trial in GVs. Donta et al. (16) conducted a large scale treatment trial of aerobic exercise training and cognitive behavioral therapy (CBT) in GVs with chronic multisymptom illnesses including persistent pain, fatigue and cognitive complaints. For VA Cooperative Study #470, 1092 Veterans were randomly assigned to Exercise (n=269), CBT (n=286), Exercise plus CBT (n=266) or usual care (n=271). Exercise training consisted of one supervised laboratory session of low intensity exercise aerobic exercise per week for 12 weeks. The exercise prescription was intended to increase physical activity levels. Exercise intensity was determined by the participant and not reported. Veterans were encouraged to exercise an additional two to three times per week during the 12 week treatment trial, but adherence to this suggestion was not reported. For CBT, Veterans met in groups with a licensed therapist once per week for 60-90 minutes. Results indicated modest improvements for both exercise and CBT with respect to physical function (11.7 % and 18.5 %, respectively), but little improvement in pain. Secondary outcome improvements for exercise were found for fatigue, distress, cognitive symptoms and mental health. Adherence to exercise was poor with a median attendance of 6 exercise sessions over the 12 week trial and only 47% considered as treatment adherent. We believe that this trial had several limitations that greatly attenuated the treatment’s effectiveness. The primary limitations were: 1) an exercise prescription requiring only one supervised session, 2) use of a non-standardized exercise prescription not designed for progressive increases in intensity, frequency or duration, 3) failure to measure physical activity when the trial was designed to increase this behavior, and 4) poor adherence to both exercise and CBT conditions. Therefore, we believe that it is premature to discount exercise training as a treatment for GVs with CMP. In fact, it can be reasonably argued that exercise “training” did not occur in this large scale study with only 6 single bouts of exercise being attended. We also agree with the statements made by Hotopf (24) that, “*Despite the importance of large pragmatic trials, additional small trials of focused treatments in specialty settings are required to develop and assess appropriate treatments for GWVI.*”, and that it is useful “...*to establish whether a treatment can work under ideal conditions before attempting to determine whether it does work in the real world.*”

We intend to apply the lessons learned from both the FM and GV exercise trials and test the efficacy of RET for GVs with CMP. Specifically, we plan to test the impact of RET on pain, physical function and patient global impression of change (PGIC) in a well-defined group of GVs meeting criteria for widespread and chronic musculoskeletal pain. We will use a standardized exercise prescription that begins gradually to avoid symptom exacerbation, includes a planned progression designed to increase muscular strength and includes measures of total work to document progression and demonstrate a training effect. We will employ a recruitment and retention plan to help ensure adequate adherence to both RET and WLC conditions. We will collect detailed measures of symptoms, adherence and adverse events using validated questionnaires and standardized procedures. We will collect measures of total physical activity to determine whether RET increases decreases or does not change physical activity behaviors. Finally, we will begin to determine how exercise impacts CMP by exploring potential central nervous system mechanisms of chronic pain maintenance.

Does RET increase, decrease or have no effect on total physical activity in GVs with CMP?

Physical activity is an important determinant of both physical and mental health (*Physical Activity Guidelines for Americans*: <http://www.health.gov/paguidelines/committeereport.aspx>). Greater total physical activity levels are associated with increased physical function, improved mental health, increased energy and decreased symptoms of chronic pain (21, 25). To our knowledge, none of the exercise training trials of chronic musculoskeletal pain have objectively measured the impact of exercise training of total daily physical activity. In fact, few studies in the general population have examined this adequately (26). Using self-reports, studies in older adults have found no changes (27) in total physical activity with exercise interventions (28), while with

objective monitoring, obese children were found to decrease their total activity (29). More recently, a study of aerobic exercise training in adults using objective measurement of activity, and careful consideration of exercise vs. non-exercise activity found no difference in activity outside the intervention (30). It's possible that changes in low-level physical activity, or in other words, a simple reduction in sedentary behavior may have a meaningful influence on pain. The lack of objective measurement has precluded testing this hypothesis. It is plausible that for chronic pain patients the adoption of a structured exercise training program reduces physical activities performed during the rest of the day. In chronic fatigue syndrome (CFS), it has been hypothesized that patients have "activity limits" and that exceeding the limit may result in symptom exacerbation (31). In FM, sedentary behaviors have been attributed, in part, to the patients' fear that acute exercise will increase their painful symptoms (32); a stark contrast to the documented benefits of chronic exercise training. Therefore, we intend to objectively quantify daily physical activity of GVs with CMP using accelerometry methods. Objective measurement of physical activity will allow us to determine whether RET increases, decreases or has no impact on total physical activity levels in GVs with CMP and will allow us to begin to characterize who benefits from RET (e.g. possibly those GVs that maintain or increase their extra-intervention physical activity).

Can RET impact well-controlled laboratory tests of pain sensitivity & regulation in GVs with CMP?

Enhanced pain sensitivity and abnormal pain regulation to experimental pain stimuli are two of the most consistent experimental findings from studies of patients with FM. These and other data have provided evidence suggesting that CMP can be maintained by central dysregulation of pain processing. To date, the evidence in favor of the benefits of exercise for patients with CMP has been based largely on self-reported symptoms. Thus, the biological mechanisms underlying how exercise improves the symptoms associated with CMP have rarely been investigated. Studies examining objective outcomes of nociceptive processing are needed to determine the impact of exercise on CNS mechanisms of pain perception and regulation.

Pain sensitivity and pain regulation in persons with chronic pain.

Although there has been little experimental research directed at examining musculoskeletal pain in Gulf Veterans, like exercise training, insight can be gained from research that has been conducted in FM. In the absence of a clear peripheral pathology, FM researchers have turned their focus to the central nervous system (CNS). Specifically, tests of the nociceptive system suggest that FM pain is associated with abnormal CNS processing of sensory stimuli; also termed central nervous system dysregulation. Several different techniques have provided convergent evidence that increased pain sensitivity to experimental pain stimuli in FM is the result of augmented nociceptive processing and that this dysregulation may play a role in the maintenance of FM pain. Psychophysical experiments have shown that FM subjects exhibit a dysregulation of diffuse noxious inhibitory controls (33), an exaggerated wind-up response to repetitive pain stimuli (34) and an absence of an exercise-induced analgesic response (35). Data from our laboratory show that GVs with CMP also exhibit exaggerated sensitivity to experimental pain stimuli and become hypersensitive following acute exercise. To our knowledge, none of the chronic exercise treatment trials in FM have tested whether exercise training has an impact upon pain sensitivity or pain regulation of experimental pain stimuli.

Functional brain imaging of experimental pain.

Psychophysical pain assessment and functional brain imaging methods recently have been applied to understand the neural representation of pain in CMP. In a well-designed study, Gracely et al. (12) reported that fMRI brain responses to experimental pressure pain, set at either similar stimulus levels or similar subjective pain levels, were augmented in FM patients compared to controls. Regions of augmentation included the primary somatosensory cortex, inferior parietal lobe, anterior cingulate cortex (ACC), secondary somatosensory cortex, superior temporal gyrus and cerebellum. These data support the view that physiological processing of pain is altered in FM. They are consistent with results from our lab examining fMRI responses to heat pain in FM (9). These data support the hypothesis that CMP is maintained by augmented processing of nociceptive information (36, 37). Our preliminary neuroimaging data in GVs with CMP also support augmented brain responses to pain. For this project, we intend to test whether RET can impact neural responses to painful experimental stimuli.

Functional brain imaging of pain and the influence of attention and distraction.

Cognitive aspects of pain, such as anticipation and attention, are important determinants of the pain experience (38). Consistent with a multidimensional pain concept involving sensory, affective and behavioral dimensions, cognitions about pain can have profound impacts on the actions taken to relieve or cope with pain (39, 40). Further, anticipation, attention, avoidance and fear have all been shown to contribute to the experience of chronic pain and may, in part, determine whether acute pain develops into a chronic problem (41).

Pain requires attention. In healthy individuals, attention directed towards pain results in more intense pain perception, while distraction from pain results in decreased pain perception (42, 43). Heightened attention to painful symptoms is also associated with greater disability and health care utilization (44).

The effects of attention and distraction on BOLD responses to pain have been studied using a variety of experimental paradigms. Derbyshire and colleagues (45) using PET and the Stroop color-word task, reported two distinct areas in the ACC (mid- and perigenual cingulate) that responded to pain and the Stroop test independently. Similarly, Valet and colleagues (46), using the Stroop color-word task found evidence of top-down regulation of pain through a “cingulo-frontal” system where activity within the perigenual ACC and orbitofrontal cortex influenced activity within the periaqueductal gray (PAG) and thalamus.

Cognitive modulation of pain appears to have both excitatory and inhibitory characteristics. Using a distracting maze task and the cold pressor pain test, Petrovic et al. (47) reported that distraction from pain resulted in increased activity in frontal cognitive regions (orbitofrontal and ventromedial prefrontal cortices) and decreases in “somatosensory association” areas (secondary somatosensory cortex and insular cortex). Attention to cognitive tasks results in decreased activity in areas involved in pain perception (insular cortex and mid ACC) and increased activity in regions involved in attention and cognition (i.e., orbitofrontal and perigenual ACC)(42). The PAG has also been shown to increase during cognitive tasks but only when combined with painful stimuli (48).

Our preliminary data suggest that changes in pain during distraction are significantly related to PAG activity in controls but not FM patients and that FM patients require greater distraction than controls to regulate their pain response. Treatments that improve pain symptoms may also improve the patients’ ability to attend to cognitive tasks. The weight of evidence from randomized controlled trials indicates that exercise training improves executive function, including better attentional control, among older adults (49). For this project, we will test whether RET can impact pain modulation in GV with CMP by delivering painful stimuli during a distracting cognitive task. If RET is beneficial, we would expect that the Veterans’ ability to distract from pain would be enhanced and the neural responses to pain will reflect this by showing increases in regions associated with pain modulation and decreases in areas associated with pain encoding.

Can RET impact pain-relevant brain white matter tracts in GV with CMP?

Diffusion tensor imaging technology is just beginning to be applied to the study of pain and the nociceptive system. Work detailing the ability to acutely image white matter tract trajectories from select thalamic subnuclei (50) shows promise for applying these methods to CMP populations where white matter tract abnormalities may be contributing to the maintenance of chronic pain. White matter tract abnormalities have been demonstrated for migraine patients (51). A recent study in FM suggests that DTI is particularly useful for understanding potential mechanisms of CMP. Sundgren et al. (52) reported that FM patients exhibited significantly decreased fractional anisotropy (FA) values in the right thalamus compared to healthy controls and that FA values within FM were significantly and negatively correlated with ratings of clinical pain and perceived pain control. Research in healthy subjects has demonstrated the utility of DTI methods for assessing potential nociceptive systems. Hadjipavlou and colleagues (53) showed that DTI could be used to demonstrate white matter tract connections between cortical and sub-cortical structures involved in pain control (i.e. prefrontal cortex, amygdala, thalamus, hypothalamus and rostroventral medial medulla) and both the PAG and nucleus cuneiformis; regions central to descending inhibitory and facilitory control, respectively. The sensitivity of DTI for tracking illness and recovery, and the relationship to disease outcomes, has recently been documented for traumatic brain injury (54) and schizophrenia (55). These studies demonstrate this methods potential clinical utility.

We will use established DTI methods to characterize white matter tract microstructure and trajectories along pain-relevant tracts originating from the thalamus, PAG, IC, orbitofrontal and perigenual cingulate cortices. These regions have been shown to interact in the top-down cognitive control of pain (16) and our

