Power estimates for the trial are based on Specific Aim 1. General multivariate regression models will be used to estimate the time averaged difference in pain ratings and clinical symptom scores (continuous measurements) between the treatment and the control group. With general multivariate regression models we model both the dependence of the response on the explanatory variables as well as the autocorrelation among the responses. In order to achieve 90% power, at alpha equal to .05, with an effect size of .6 (minimum effect size of clinical importance) and with a correlation of .6 between measurements from each individual, the necessary sample size would be 34 subjects per group. If we take into account a 20% subject attrition rate, then the total sample size should be 41 subjects per group. All randomized subjects will be included in the analysis within the appropriate arm that they were randomly assigned (i.e. an intent-to-treat analysis will be used). Noncompliance, protocol deviations, withdrawal or any other problem that occur after randomization will be ignored and the participant's last observed data points will be carried forward in the analyses. Missing data will be assumed to be missing completely at random and appropriate missing data methods will be used (i.e. multiple imputation) to minimize the effect of withdrawal. For the purpose of evaluating Specific Aim 2, a similar methodology will be employed to estimate the time averaged difference in physical activity counts as measured by accelerometry.

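### The plan promises to tell 'no impact' of RET on total physical activity from an increase or decrease, but sets no margin or interval rule that could support 'no impact'

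*Combined protocol and SAP*

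**What the plan says.** The three-way aim is stated repeatedly. The introduction says: "Objective measurement of physical activity will allow us to determine whether RET increases, decreases or has no impact on total physical activity levels". The Background section on whether RET changes total activity repeats it: "determine whether RET increases, decreases or has no impact on total physical activity levels in GVs with CMP". The Background section on the efficacy of RET says much the same, with 'does not change' as the third outcome. In Specific Aims and Hypotheses, Aim 2 concerns the influence of RET on total daily activity. Hypothesis 2 predicts an increase that comes entirely from the RET itself, which implies no change in activity outside the sessions.

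Under Statistical Considerations, Aim 2 gets one sentence: "a similar methodology will be employed to estimate the time averaged difference in physical activity counts as measured by accelerometry". The method it refers to is the Aim 1 comparison of treatment and control. "Power estimates for the trial are based on Specific Aim 1", and no power, margin or smallest change of interest is given for activity.

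**The concern.** A difference analysis can support 'increases' or 'decreases'. It supports 'no impact' only if the interval for the difference is read against a limit for what counts as negligible, and the plan sets no such limit. Without one, the outcome most naturally read as 'no impact' is a non-significant difference, which may only reflect limited precision.

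This matters because the introduction and Background both call it plausible that structured training displaces activity during the rest of the day. A non-significant result need not exclude a reduction of that kind. The 'entirely' in Hypothesis 2 needs a no-change criterion for the same reason. The point holds whether or not session activity is separated from the rest of the day.

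**Working it through.** **Inputs from the documents.** Statistical Considerations gives alpha .05 ("at alpha equal to .05", sidedness not stated), 90% power, effect size .6, 34 per group, and 41 per group after 20% attrition; the correlation enters as "with a correlation of .6 between measurements from each individual". The Subjects section recruits 34 per group. Taking 20% attrition from 34 leaves 34 × .8 ≈ 27. Activity weeks are baseline, weeks 5, 10 and 16, and the 6- and 12-month follow-ups.

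**Assumptions.** The correlation ρ = .6 is stated for Aim 1; using it for accelerometer counts is an assumption. The test is taken as two-sided because the question covers both directions. The number of averaged measurements, m, is not stated; 3 is the number during treatment, and 4 is shown for sensitivity. The benchmarks of 0.5 and 0.3 SD are ours.

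**The plan's own figure.** The variance of an average of m measurements, in SD² units, is V = (1 + (m−1)ρ)/m, which is .733 for m = 3 and .70 for m = 4. By the normal approximation, n = 2V(z₁₋α + z.90)²/.6² per group.
- One-sided .05, m = 4: 2 × .70 × (1.645 + 1.282)²/.36 = 33.3, so 34, as stated. m = 3 gives 35.
- Two-sided .05, m = 4: 2 × .70 × (1.960 + 1.282)²/.36 = 40.9, so 41. m = 3 gives 43.

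**Chance of missing a true change δ.** The noncentrality is λ = δ/√(2V/n), with 2n−2 degrees of freedom and a two-sided .05 t test. V depends on how baseline is used:
- unadjusted: V = .733 (m = 3), .70 (m = 4)
- change from baseline: V + 1 − 2ρ = .533, .50
- baseline as covariate: V − ρ² = .373, .34

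Example: n = 34, m = 3, unadjusted, δ = .5 gives λ = .5/√(2 × .733/34) = 2.41 and a miss rate of 34%.

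| Per arm | Model | 0.5 SD missed (m = 3, 4) |
|---|---|---|
| 34 | unadjusted | 34%, 32% |
| 27 | unadjusted | 44%, 42% |
| 41 | unadjusted | 26%, 24% |
| 34 | change score | 21%, 18% |
| 34 | baseline as covariate | 9%, 6% |

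For δ = .3 at 34 per arm, the miss rate is 70%, 69% unadjusted and 49%, 45% with baseline as covariate.

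**Sensitivity to ρ** (34 per arm, m = 3-4, δ = .5, normal approximation). Unadjusted, the miss rate is 15-19% at ρ = .3, 26-29% at ρ = .5 and 39-40% at ρ = .8. With baseline as covariate it is 9-13%, 8-11% and about 1%.

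**Interval width.** The 95% half-width, t.975 × √(2V/n), at 34 per arm is 0.41-0.42 SD unadjusted (m = 4, 3) and 0.28-0.30 SD with baseline as covariate.

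**Chance of meeting a 0.5-SD margin when the true difference is zero.** The condition is that the 90% interval, D ± t.95 × SE, lies wholly inside ±0.5 SD. At 34 per arm with m = 3-4, the chance is 54-57% unadjusted, 75-79% with change scores and 91-94% with baseline as covariate.

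**The case against.** The strongest reply is that the three-way phrase is background rationale and an ordinary way to pose a two-sided question. Hypothesis 2 is directional, Aim 2 did not size the trial, and no equivalence test is promised. The analysis sentence speaks of estimating a difference, so an interval may well be reported. Part of this stands: a reader might infer that the sponsor will report any p > .05 as 'no impact', but the documents state no such rule. What remains is that the promise of a 'no impact' answer is made repeatedly, and an interval alone does not settle it without a limit to read it against.

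A second reply concerns size, and it is correct. A reader might infer that the trial would miss a half-SD change in about a third of trials or more. The documents do not support this as a floor. They fix neither sidedness, nor m, nor baseline adjustment, nor which of 34 and 41 per group applies. Baseline accelerometry is scheduled, and the Summary of Experimental Design bases the primary aims on baseline compared with end of treatment, so using baseline is plausible. A one-sided test, which best reproduces the stated 34, would miss 0.5 SD in 21-23% of trials unadjusted, but could not detect a change in the other direction. For the same reason, 54-57% is not a ceiling on the chance of showing equivalence.

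It is also fair that m = 4 is not clean. A fourth measurement is either baseline, which dilutes the effect, or a follow-up after WLC completers have been offered training.

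**Conclusion.** The point stands in structure: the plan promises a 'no impact' conclusion but provides no criterion that could support it. Its size is conditional. With ρ = .6 carried over from Aim 1, a two-sided .05 test and 3-4 measurements, a 0.5-SD change is missed in anywhere from 6-9% (34 per arm, baseline as covariate) to 42-44% (27 per arm, unadjusted) of trials. Under the most favourable of the three models at 34 per arm, a 0.3-SD change is still missed in nearly half of trials, so non-significance alone does not show 'no impact'. The documents give no meaningful activity change, so neither benchmark is the sponsor's.

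**What to change.** Add to the Aim 2 paragraph of Statistical Considerations, before unblinding:
- A margin for the RET minus WLC accelerometer difference, in counts per day, justified by the sponsor. The 0.5 SD used here is only an example.
- The difference will be reported with its confidence interval.
- 'No meaningful impact' will be concluded only if the 90% interval lies wholly inside the margin. Otherwise a non-significant result is inconclusive.
- The sidedness of the test, the measurements averaged, the use of baseline, and the number per arm, with the 34 and 41 reconciled.
- If the chance of meeting the margin is quoted, it is given for the model actually chosen.

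The data and sample stay the same, and only wording changes. The cost is that some results that would have been called 'no impact' become inconclusive. A margin chosen after the results are known would carry little weight, so it belongs in the plan now.
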